Study design overview. This is a single-blinded, pilot randomized controlled trial of 48 Medicare patients referred to HHC for skilled rehabilitation services. Twenty-four patients will be randomly assigned to the treatment-as-usual arm and receive usual rehabilitation services. The other 24 patients in the experimental arm will receive the ADL-enhanced program in six OT visits as well as usual rehabilitation services.

Selection and Enrollment of Participants

Participants will be recruited from partnered home health agencies

Inclusion criteria. Patients are eligible to the study if they are:

- (1) \geq 65 years of age,
- (2) Medicare beneficiaries,
- (3) referred for skilled rehabilitation services; and
- (4) diagnosed with three or more comorbidities.

Exclusion criteria. Patients are ineligible if they have contraindications for moderate-intensity exercise, which include:

- acute fractures with surgical or weight-bearing restrictions,
- elective joint replacement surgery,
- lower extremity amputation,
- active treatment for cancer diagnosis,
- on-going dialysis treatment,
- acute cardiac surgery,
- acute stroke or a major neurologic disorder limiting motor movements,
- terminal stage of congestive heart failure,
- a referral to hospice care, or
- severe cognitive deficits limiting verbal communication.

Enrollment Procedures.

Screening procedure. The home health care team will obtain verbal permission from new patients to allow the research coordinator to contact and screen the new patients via phone. The coordinator will record the screening results (fail or pass) on a screening log. The coordinator will call the eligible patient, verify the eligibility, and introduce the study.

Consent procedure. The coordinator will then conduct a recruitment home visit to the eligible patient and obtain consent at the end of the visit. If the patient does not provide consent during the recurrent home visit but decides to participate in the study afterwards, a study outcome assessor will obtain consent at the beginning of the baseline assessment visit. Reasons of rejection will be recorded.

Patients who are eligible and agree to participate will be referred to the study outcome assessor, who will schedule the patient within 48 hours to obtain the consent, if not yet obtained by the research coordinator, and complete the baseline assessments (ADL and physical functioning assessments) at the participant's home. The assessor will be blinded to group assignments.

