Saint Louis University Mental Status Exam	x			

Patient demographic background and medical info from self-report as well as chart review	x			
Patient satisfaction survey		x		
Adverse events (hospitalization, falls, emergency room visits)		x	x	x

+: The end of ADL-enhanced program, the last home visit of usual care, or 6 weeks from the baseline assessment, which occurs last.

Study visit schedule.

Description of Evaluations.

Screening evaluation.

The screening will occur over the phone within three business days after a home health care provider has mentioned the study opportunity to the patient and received verbal permission from the patient for the research coordinator to contact him/her. The research coordinator will follow a phone script approved by the UF IRB for this phone screening. The coordinator will obtain a verbal permission prior to proceeding with screening questions from the potential research participant after a brief introduction of the study. These screening questions are:

1. Are you aged 65 years or above?
2. How many medical conditions, including chronic conditions, that you currently have? Examples of the conditions include but not limit to diabetes, heart disease, high blood pressure, joint disease or arthritis, and lung disease.
3. Do you have any of the following conditions?
 - an elective joint replacement surgery in the last month
 - orthopedic or heart surgery in the last month
 - lower extremity amputation
 - currently receiving treatment for cancer
 - an ongoing dialysis treatment
 - a neurologic condition, such as stroke or Parkinson's disease, that significantly limits your movements
 - congestive heart failure that is at the terminal stage

In addition to these questions, the interviewer will administer the "Six-item cognitive screener" to determine the potential participant's cognitive ability. If a participant scores a 4, 5, or 6 on the screener, they will be eligible for the study.

Enrollment, baseline, and randomization.

Enrollment. A patient is considered enrolled in this study when he or she meets the eligibility criteria and signs the informed consent form.

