Consenting process. If the patient passed the screening, the research coordinator will then conduct a recruitment home visit to the eligible patient within five business days. During the visit, the coordinator will provide the patient with a detailed description of the research study and go over the informed consent process. If the patient does not provide consent during the recurrent home visit but decides to participate in the study afterwards, a study outcome assessor will obtain consent at the beginning of the baseline assessment visit. If the patient decided not to enroll, the reason(s) of rejection will be recorded.

Baseline assessment. The enrolled patient will be then referred to the study outcome assessor, who will schedule the patient to obtain the consent, if not yet obtained by the research coordinator, and complete the baseline assessments at the participant's home. The baseline assessment should occur within seven business days of the recruitment visit. The assessor will be blinded to patient group assignments. The blinded outcome assessor will conduct the following assessments during the baseline evaluation visit. These assessments are listed in suggested order. The outcome evaluator will alternate between self-reported assessments and performance-based assessments as well as upper extremity performance tests and lower extremity performance tests to reduce the testing burden for patients. Additionally, short breaks (one to five minutes) between assessments will be provided to patients as needed.

1. Demographic information of age, gender, race/ethnicity, chronic conditions, and number of medications
2. Assessment of Motor and Process Skills
3. Activity Measure of Post-Acute Care Home Health Short Form
4. Jebsen Hand Function Test
5. Box and Block Test
6. PEG three-item scale
7. Patient Health Questionnaire-9
8. Timed-Up-and Go
9. Short Physical Performance Battery
10. Saint Louis University Mental Status Exam.

The research coordinator will extract the patient's OASIS self-care item scores (scores at the start of care and discharge) from medical chart when the patient has been discharged from home health care or 60 days after admission.

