Randomization. Randomization will occur after the baseline assessment. [name] (Co-I) will generate a randomization list using a computer software and seal the list in opaque envelopes. The on-site research coordinator will open one envelope after a patient has completed the baseline assessments. If the patient is assigned to the ADL-enhanced group, the coordinator will notify the study OT to start intervention.

Post-intervention evaluation.

The satisfaction survey will be given to the patient in the experimental group after the last visit of ADL-enhanced intervention by the research coordinator over the phone.

For the group that will receive the ADL-enhanced program, the post-intervention evaluation conducted by the blinded outcome assessor will occur within seven business days after the completion of the last visit of usual home health rehabilitation therapy or ADL-enhanced intervention, whichever occurs last. For the control group, the post-intervention evaluation conducted by the blinded outcome assessor will occur either 6 weeks after the baseline assessment or after the last usual home health visit, whichever occurs last. Patients will be instructed not to discuss their therapy content with the blinded outcome assessor and vice versa. The following assessments will be administered during the post-intervention evaluation visit.

1. Assessment of Motor and Process Skills
2. Activity Measure of Post-Acute Care Home Health Short Form
3. Jebsen Hand Function Test
4. Box and Block Test
5. Timed-Up-and Go
6. Short Physical Performance Battery
7. Adverse events questionnaire

The research coordinator will extract the patient's OASIS self-care item scores (scores at the start of care and discharge) from medical chart when the patient has been discharged from home health care or 60 days after admission.

One-month follow-up evaluation.

The one-month follow-up evaluation conducted by the blinded outcome assessor will occur within seven business days one month after the completion of the last visit of usual home health rehabilitation therapy or ADL-enhanced intervention (Day 30 post intervention), whichever occurs the last. Patients will be instructed not to discuss their therapy content with the blinded outcome assessor and vice versa. The following assessments will be administered during the one-month follow-up evaluation visit.

1. Assessment of Motor and Process Skills
2. Activity Measure of Post-Acute Care Home Health Short Form

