3. Jebsen Hand Function Test
4. Box and Block Test
5. Timed-Up-and Go
6. Short Physical Performance Battery
7. Adverse events questionnaire

Final evaluation or three-month follow-up evaluation.

The final evaluation will occur over the phone by the research assistant or coordinator within seven days three months after the completion of the last visit of usual home health rehabilitation therapy or ADL-enhanced intervention (Day 90 post intervention). The following assessments will be administered during the final evaluation.

1. Activity Measure of Post-Acute Care Home Health Short Form
2. Adverse events questionnaire

Data analysis plan.

Preliminary analysis. We will compare participant demographics and covariates (e.g., pain levels) between the two groups. Variables with statistically significant differences will be included in the subsequent statistical models as covariates. We will graph spaghetti plots for repeated measurements and examine for outliers.

Data analysis. Since ADL and physical functioning outcomes will be collected over three time points (baseline, post-treatment, one-month follow-up), the mixed-effects linear regression modeling will be conducted to fit the data, in which a random-effects term is included to accommodate within-subject data correlation and a quadratic growth curve is included to describe the temporal trend of the response.

For **Aim 1**, which will estimate the preliminary effect of the ADL-enhanced program on improving ADL, three separate mixed-effects regression analyses will be conducted for the Motor Skills scores of the Assessment of Motor and Process Skills (the primary outcome), the Activity Measure of Post-Acute Care Home Health Short Form, and the OASIS self-care items, in each of which sex, race, age, and other covariates will be included in the model.

For **Aim 2**, which will estimate the preliminary effect of the ADL-enhanced program on physical functioning of the upper extremity and lower extremity, four similar separate analyses will be conducted for the Box and Block Test, Jebsen Hand Function Test, Timed-Up-and Go, and Short Physical Performance Battery.

For **Aim 3**, the program completion rate and satisfaction rate will be compared to the benchmark, 75%. Fisher's Exact Test will be performed to compare the proportion of patients who experience adverse events of hospitalization, emergency room visits, or falls (adverse event rate) between the two groups.

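### Adverse events rest on a questionnaire at three contacts, with death unlisted and no second source or rule for patients who miss it, so events after the last completed contact are missed

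*Combined protocol and SAP*

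**What the plan says.** The adverse-event row of section 6.1, Schedule of Evaluations, reads "Adverse events (hospitalization, falls, emergency room visits" and is marked at post-intervention, one month and three months. The instrument is an item in the assessment lists: "7. Adverse events questionnaire" at the post-intervention and one-month visits, and "2. Adverse events questionnaire" at the three-month telephone call. No other source of events is described.

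The footnote to the schedule sets post-intervention at the latest of three dates, one of which is six weeks from baseline.

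The coordinator also opens each patient's chart during follow-up, but only for OASIS self-care scores, "from medical chart when the patient has been discharged from home health care or 60 days after admission" (Baseline assessment and Post-intervention evaluation). Other chart review is marked at baseline only.

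For Aim 3 the Data analysis plan states: "Fisher's Exact Test will be performed to compare the proportion of patients who experience adverse events of hospitalization, emergency room visits, or falls". Hypothesis 2b predicts fewer patients with these events in the experimental arm at one and three months. Mortality appears only in the Background. The plan gives no denominator, no rule for a missed questionnaire, no proxy respondent and no handling of death or withdrawal.

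**The concern.** Fisher's test needs each patient classified as having an event or not. A patient who dies, or who is admitted and then withdraws, cannot report that event at the next contact. Absence is then plausibly caused by the outcome being counted. The enrolled patients are aged 65 or over, have three or more comorbidities and have been referred for skilled rehabilitation, so such losses are credible.

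A patient lost before the first contact contributes no adverse-event information at all, and that contact comes some six weeks in. Losses may also differ by arm, because only the experimental arm has six additional therapy visits. This is the only between-arm safety comparison in the plan, and each arm has 24 patients, so a few unobserved patients matter.

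**Working it through.** **Inputs from the documents.** Arm sizes are in the Study design overview. For control it states: "Twenty-four patients will be randomly assigned to the treatment-as-usual arm and receive usual rehabilitation services". It allots the same number to the experimental group, so the total is 24 + 24 = 48. The documents give no event rate, dropout rate, significance level or power for this comparison, so there is no figure to reproduce. Every event count below is an assumption. Tests are two-sided Fisher's exact.

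**Weight of one patient.** 1/24 = 4.2 percentage points.

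**Effect of unobserved event patients.** If k patients in an arm with x events of 24 had an event but gave no questionnaire, that arm shows (x − k)/(24 − k) when they are left out, or (x − k)/24 when they are taken as event-free.

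| Assumed truth (control vs experimental) | Unobserved event patients | Left out | Taken as event-free |
|---|---|---|---|
| 10/24 vs 3/24: 29.2 points, p = 0.049 | 2 control | 8/22 vs 3/24: 23.9 points, p = 0.086 | 8/24 vs 3/24: 20.8 points, p = 0.168 |
| same | 2 experimental | 10/24 vs 1/22: 37.1 points, p = 0.005 | 10/24 vs 1/24: 37.5 points, p = 0.004 |
| 8/24 vs 4/24: 16.7 points, p = 0.318 | 4 control | 4/20 vs 4/24: 3.3 points, p = 1.000 | 4/24 vs 4/24: 0 points, p = 1.000 |
| same | 2 experimental | 8/24 vs 2/22: 24.2 points, p = 0.074 | 8/24 vs 2/24: 25.0 points, p = 0.072 |
| same | 4 experimental | 8/24 vs 0/20: 33.3 points, p = 0.005 | 8/24 vs 0/24: 33.3 points, p = 0.004 |
| same | 2 in each arm | 6/22 vs 2/22: 18.2 points, p = 0.240 | 6/24 vs 2/24: 16.7 points, p = 0.245 |

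Loss in the control arm shrinks the apparent benefit and loss in the experimental arm enlarges it. In the last row, where loss is equal, the difference hardly moves.

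**Not every such loss changes the test.** With 9/24 = 37.5% in both arms and three event patients unobserved in one, that arm shows 6/21 = 28.6% or 6/24 = 25.0%. The spurious gap is 8.9 or 12.5 points, but p = 0.75 or 0.53. Taking the three as event-free gives the larger distortion.

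**What the chart could cover.** Take post-intervention at its six-week minimum, 42 days after baseline. The one-month contact is then about day 42 + 30 = 72 and the three-month contact about day 42 + 90 = 132, before visit windows. A chart read 60 days after agency admission, which precedes baseline, ends before day 60. It would cover most or all of the period before the first contact, but leave more than 72 − 60 = 12 days uncovered before the second and more than 132 − 60 = 72 days before the third. If it is read at an earlier discharge, it covers less.

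**The case against.** A reader might infer that patients who die, withdraw or cannot be reached are excluded from the comparison. The documents do not say so. They state no exclusion rule and no denominator, and they neither provide for nor rule out a proxy respondent. What can be said is that no source or rule exists for a patient without a questionnaire.

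A reader might also infer that such a patient's events are all lost. That holds only for loss before the first contact. An event reported earlier can still count in a cumulative any-event analysis. The loss concerns events after the last completed contact.

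Nor do the documents support the inference that the bias favours the new programme. More loss under usual care would hide a benefit. The illustrative counts are assumed, and on some of them the planned test stays far from significance.

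Two objections concern the remedy, and both stand as limits on it. The chart covers little of the one- and three-month period that Hypothesis 2b addresses, and the documents do not show how fully it records emergency visits and falls. The extractor is also the coordinator who opens the allocation envelope. Finally, adding death changes what Hypothesis 2b measures, so the three-event result should be kept beside it.

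This is a secondary aim of a pilot, which limits the weight of the point. None of these objections supplies a source for the missed events.

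**Conclusion.** The concern holds in this form. As written, the plan has one route to an adverse event, does not list death, and has no provision for a patient who does not answer. Events after the last completed contact, including those that cause the loss, are missed in the Aim 3 comparison, and the direction of the resulting bias cannot be known in advance.

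The only part of its size that the documents fix is 4.2 points per patient in an arm of 24. That two to four unobserved event patients can remove or create an apparent difference is an illustration. It rests on assumed event counts and on the losses falling in one arm. The point should be dealt with before analysis, but it implies no change to the sample size.

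**What to change.** 1. At the chart extraction already scheduled (agency discharge or 60 days), record dated hospital admissions, emergency visits and falls, with the same fields in both arms. Count a patient as having an event if either the chart or the questionnaire shows one.
2. Report deaths by arm and count a randomised patient who dies as having an event. Show the three-event result without death beside it.
3. Report all 48 randomised patients by arm. For each period, state how many have neither a questionnaire nor a charted event, and do not code them as event-free by default. Give best-case and worst-case sensitivity analyses. For example, with 8 observed events in 22 control patients, two control patients unobserved and 3/24 in the experimental arm, the bounds are 8/24 versus 3/24 (20.8 points, p = 0.168) and 10/24 versus 3/24 (29.2 points, p = 0.049).

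**Cost.** A few extra chart fields and a short addition to the analysis plan. Event rates will be slightly higher. The extraction is done by a coordinator who knows the allocation; identical dated fields limit that problem but do not remove it. Events after the chart window still rest on self-report, which is why the bounds in step 3 are needed.

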Hypothesis: Patients who receive the ADL-enhanced program plus usual rehabilitation therapy will show greater improvements in the Motor Skills scores of the Assessment of Motor and Process Skills (the primary outcome), Self-care items in the Outcome and Assessment Information Set (clinical outcome), and Activity Measure for Post-Acute Care Home Health Short Form (patient-reported outcome) at treatment completion and less decline at 1-month and 3-month follow-up than usual rehabilitation therapy.

Secondary Objectives.

Secondary objective 1: To estimate the preliminary effect of the ADL-enhanced program on improving physical functioning at treatment completion and one month after the completion.

Hypothesis 1: Patients who receive the ADL-enhanced program plus usual rehabilitation therapy will show greater improvements in the Box and Block Test (upper extremity physical function), Jebsen Hand Function Test (upper extremity physical function), Timed-Up-and-Go Test (lower extremity physical function), and Short Physical Performance Battery (lower extremity physical function) at treatment completion and less decline at one-month follow-up than usual rehabilitation therapy.

Secondary objective 2: To assess the completion, satisfaction, and adverse event rates of the ADL-enhanced program.

Hypothesis 2a: We hypothesize that the program completion and satisfaction rates will be greater than 75%.

Hypothesis 2b: Fewer patients who receive the ADL-enhanced program will have hospitalizations, emergency room visits, and falls than patients who receive usual rehabilitation therapy at 1-month and 3-month follow-up.

Background and Rationale

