Restorative approach procedures. The study OT will deliver the restorative approach starting at the 3rd visit. The selected self-care tasks include any in-home activities that the patient does to take care of self and others, which are not limited to basic ADL. In the beginning of each visit, the study OT and the patient together identify 2 or 3 activities where the patient has experienced limitations or difficulties. The study OT will apply one or two activity grading principles to each selected activity. The intervention intensity will be kept at the moderate level (somewhat hard) using the Omni Scale, which is a rated perceived exertion scale. For example, if a patient experiences difficulty to returning pantry items to overhead shelves, the study OT can let the patient wear a weighted wrist cuff while sorting pantry items (increase the load), restore items to an overhead versus shoulder-high shelf (increase the movement distance), restore items into different locations on the shelves (change of movement direction), speed up while storing items (increase the movement speed), store 10 pantry items versus store five items at a time (increase the endurance), or carry groceries with a shopping bag and store pantry items from the groceries to the overhead shelves (increase the activity complexity by combining two tasks, carrying groceries and sorting the pantry items after shopping). Patients will practice each selected task for 15 to 20 minutes with a rest break if needed.

Allowed interventions. All participants will receive the care plan approved by their home health agency. The care plan should include regular home health rehabilitation therapy.

Adherence Assessment. The adherence for the ADL-enhance intervention will be evaluated by the number of sessions that the patient is able to complete within the study period (60 days).

Study Procedures.

[figure not shown]
6.1. Schedule of Evaluations.

	Baseline	Post-intervention (Post intervention \pm 7 Business days) ⁺	One-month follow-up (Day 30 post intervention \pm 7 Business days)	3-month follow-up (Day 90 post intervention \pm 7 Business days)
Assessment of Motor and Process Skills	x	x	x	
Activity Measure for Post-Acute Care Home Health Short Form	x	x	x	x
OASIS self-care items from chart review	x	x		
Box and Block Test	x	x	x	
Jebesen Hand Function Test	x	x	x	
Timed-Up-and-Go Test	x	x	x	
Short Physical Performance Battery	x	x	x	
PEG three-item scale	x			
Patient Health Questionnaire-9	x			

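### OASIS self-care is scheduled and hypothesised as a baseline-to-treatment-completion outcome, but its two scores come from agency start of care and agency discharge, and the planned growth model does not fit them

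*Combined protocol and SAP*

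**What the plan says.** In the Schedule of Evaluations (6.1), the row "OASIS self-care items from chart review" is marked at Baseline and Post-intervention and nowhere else. The table's footnote defines the post-intervention point as "The end of ADL-enhanced program, the last home visit of usual care, or 6 weeks from the baseline assessment, which occurs last".

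The hypothesis under the Primary Objective lists OASIS self-care beside AMPS Motor Skills and the AM-PAC short form. It expects greater improvement in all three at treatment completion, and less decline at the one-month and three-month follow-ups.

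The Baseline assessment and Post-intervention evaluation sections give the same collection rule. The coordinator collects "OASIS self-care item scores (scores at the start of care and discharge) from medical chart when the patient has been discharged" by the agency; the alternative trigger is day 60 after admission.

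The Data analysis plan describes ADL outcomes as collected at three time points. It specifies a mixed-effects linear regression with a quadratic growth curve and names OASIS as one of the three Aim 1 analyses.

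**The concern.** The schedule and hypothesis describe one pair of time points, and the collection rule supplies another. If the plan is followed as written, a discharge score will be reported as an effect at treatment completion.

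This matters for interpretation. In a 48-patient pilot meant to give preliminary effect estimates, a weak OASIS result beside a better AMPS result could be read as absence of clinical benefit when part of the difference is timing. The report would hold nothing to tell the two apart, because the plan does not ask for the discharge date relative to randomisation or to the study visits.

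**Working it through.** The plan gives no figure to reproduce here. The check sets the timing rules side by side.

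**1. The first score precedes baseline.** Enrolment starts inside the agency: "The home health care team will obtain verbal permission from new patients". Phone screening follows within 3 business days (Screening evaluation) and the recruitment visit within 5 (Consenting process). Then "The baseline assessment should occur within seven business days of the recruitment visit". The upper limit from the provider's mention of the study to baseline is 3 + 5 + 7 = 15 business days, or 21 calendar days without holidays. Enrollment Procedures instead gives 48 hours for the last step. On that wording the limit is 8 business days (10 to 12 calendar days) + 2 = 12 to 14 days. The interval from start of care to the provider's mention is not stated. The order is therefore clear, but the size of the gap is not.

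**2. Effect of that gap on the comparison.** Let S be the start-of-care score, D the discharge score, and B the score the patient would have had at study baseline. Then D − S = (D − B) + (B − S). The term B − S is settled before randomisation, so its expected value is the same in both arms and it cancels from the difference in means. It can add variance. It does not shift the contrast.

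**3. The second score is not tied to the programme.**
- Study visits: six over 6 weeks, starting after randomisation, separate from usual therapy, with a 21-day window to resume (Study Intervention).
- Assessor visit (AMPS, AM-PAC): timed from the latest of the listed events, so it waits for the programme to end.
- OASIS: timed by agency discharge, with extraction at discharge or 60 days after admission.

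The assessor rule itself allows for usual care ending before the study visits. When that happens, AMPS and AM-PAC wait and the OASIS discharge score need not.

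**4. Size.** Let p be the share of experimental-arm patients scored before their last study visit, and g the mean share of the full effect they have not yet reached. The proportional loss against a completed-programme effect is p × g. The documents give no length of usual care, no discharge dates and no relation between visits and benefit, so neither p nor g can be filled in. If p = 0 the loss is nil; otherwise it can lie anywhere up to p.

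**5. Model.** A quadratic mean curve has three parameters per arm (level, slope, curvature). Two scheduled OASIS scores give two means per arm, so 3 > 2 and the curve is not identified. If actual days were used as the time scale, curvature would rest on differences between patients in time to discharge, not on any within-patient trend. The plan does not say how time is coded.

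**The case against.** The strongest defence is that start of care to discharge is a sensible clinical outcome. The Abstract and Background frame the problem as lack of ADL improvement by discharge, the source of the scores is stated twice, and the schedule row says they come from chart review. On that view only the column labels and the treatment-completion wording are wrong, and there is no dilution against a discharge estimand. Most of this stands, and it is why the remedy keeps the data and changes the claim. It does not rescue the hypothesis as worded or the quadratic model.

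A reader might infer more than the documents support:

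- **That the programme must outlast the 60-day point.** This needs the enrolment windows near their maximum or a long pause in visits. It also treats admission as the day the study is mentioned. With the 48-hour wording and no pause, the programme ends by day 54 to 56 (12 to 14 + 42) on that same assumption. Adherence Assessment counts sessions within a 60-day study period whose start is not given. Day 60 is also an extraction time, so it does not show when OASIS was scored.
- **That a stated fraction of the effect is lost.** Any such figure needs assumed discharge dates and benefit proportional to visits. The Background says the compensatory phase comes first so that patients engage in ADL at once, which fits poorly with proportionality.
- **That the early first score biases the result.** Step 2 shows that it does not.
- **That the three Aim 1 outcomes must share one estimand.** They are different kinds of measure, analysed separately.

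**Conclusion.** The mismatch is real and the plan is wrong as written on two counts. It would report a discharge score as a treatment-completion effect, and it puts a two-score outcome into a three-time-point quadratic model. Both follow from the text without assumptions.

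Dilution is possible but not established. It requires that some experimental-arm patients are discharged before their last study visit and that benefit is still accruing then. Its frequency and size are unknown.

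The scope is one non-primary Aim 1 outcome in a pilot. AMPS Motor Skills is taken by the study assessor at the study visits and is not touched. This should be corrected before analysis, but it does not threaten the trial's main estimate.

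**What to change.** 1. In the Schedule of Evaluations and the primary hypothesis, label OASIS as a start-of-care-to-discharge outcome and drop its treatment-completion claim. The same sentence's follow-up claims should also exclude OASIS, which has no follow-up score.
2. Analyse the discharge score by ANCOVA with the start-of-care score and the planned covariates, outside the quadratic growth model.
3. Report days from randomisation to discharge by arm and, for the experimental arm, the number of study visits delivered by then. Discharge happens after randomisation, so its timing could differ between arms.
4. State which score is used for a patient still under agency care 60 days after admission, and reconcile the 48-hour and seven-business-day wordings for the baseline visit.

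The cost is small: wording, one simpler model, and dates. The chart is already reviewed and completed sessions are already counted for adherence, so only the discharge and session dates need to be kept with them. There is no added patient burden. The downside is that OASIS no longer supports a claim at treatment completion.
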